11. QUALITY CONTROL AND QUALITY ASSURANCE

During study conduct, the Sponsor or its agent will conduct periodic monitoring reviews (in person or remote) to oversee the progress of the clinical trial and to ensure that it is conducted, recorded, and reported in accordance with the protocol, Standard Operating Procedures (SOPs) as applicable, Good Clinical Practice (GCP), and the applicable regulatory requirement(s).

The Sponsor representative may review source documents to confirm that the data recorded on CRFs/eCRF is accurate. The investigator and institution will allow Sponsor's representative or its agents, and appropriate regulatory authorities, direct access to source documents to perform this verification.

The study site may be subject to review by the institutional review board (IRB)/independent ethics committee (IEC), and/or to quality assurance audits performed by Sponsor, and/or to inspection by appropriate regulatory authorities.

It is important that the investigator(s) and their relevant personnel are available during any in-person monitoring visits and possible audits or inspections, and that sufficient time is devoted to the process.

12. ADMINISTRATIVE REQUIREMENTS

12.1. Protocol Amendments and Administrative Changes

Amendments and administrative changes are not to be made to this protocol without consultation with and the agreement of the Sponsor. The investigator and Sponsor should discuss amendment or administrative change. If agreement is reached, such amendment or administrative change will be developed in writing by the Sponsor and submitted to the investigator.

The investigator will be responsible for ensuring that all protocol amendments are approved in writing by the appropriate IRB or IEC before the institution of the changes specified in the amendment (except when necessary to eliminate an immediate hazard to the subjects). The investigator will also ensure that the Sponsor receives a copy of the written IRB or IEC approval of these changes.

The investigator will be responsible for ensuring that the IRB or IEC receives written notification of all administrative changes to the protocol prior to institution of the specified changes. The investigator will ensure that the Sponsor receives a copy of these written notifications.

12.2. Data Handling and Record Keeping

The investigator will document all study related procedures directly on the source record or medical chart as the primary source of data collection. Study related information/data points required by the sponsor for analysis will be transcribed by the investigator or designee from the source record, onto the CRF/eCRF (data collection tool) for this study using good documentation practices.

In some instances, the sponsor will provide a CRF template for use as the primary source of data collection.

The investigator is encouraged, however, not required to maintain additional source records on matters respective to the subject's safety and wellbeing not already captured on the CRFs/eCRF or source template.

Black or blue ink must be used on all data collection requirements. All errors and omissions must be crossed out by means of a single line, and the date and initials of the correction or addition of correct information must be provided. Use of white-out or write-overs will not be permitted. All study related records will be kept in a secure and locked location and shall only be accessible to the assigned study personnel during the conduct of the study, and to the regulatory authorities in the event of an inspection.

All raw and analyzed data files will be stored electronically on a private Google Drive folder that is accessible only to study staff. This folder is password protected and requires permission for outside entities to access its files.

12.3. Case Report Forms / Electronic Data Record

As used in this protocol, the term case report form (CRF) should be understood to refer to either a paper form or an electronic data record or both, depending on the data collection

method used in this study.

A CRF is required and should be completed for each enrolled subject. The completed original CRFs are the sole property of the sponsor and should not be made available in

any form to third parties, except for authorized representatives of the sponsor or appropriate regulatory authorities, without written permission from the sponsor.

It is the investigator's responsibility to ensure completion, review and approve all CRFs. CRFs must be signed by the investigator or by an authorized staff member. These signatures serve to attest that the information contained on the CRFs is true and accurate.

At all times, the investigator has final personal responsibility for the accuracy and authenticity of all clinical and laboratory data entered on the CRFs. In cases where the source documents are the hospital or the physician's chart, the information collected on the CRFs must match those charts.

12.4. Record Retention

To enable evaluations and/or audits from regulatory authorities or the Sponsor, the investigator agrees to keep records including the identity of all participating subjects (sufficient information to link records, e.g., CRFs and hospital records), all original signed informed consent forms, copies of all CRFs, serious adverse event forms, source documents, and detailed records of treatment disposition. The records should be retained by the investigator according to ICH guidelines, local regulations, or as specified in the Clinical Study Agreement, whichever is longer.

If the investigator relocates, retires, or for any reason withdraws from the study, the Sponsor should be prospectively notified of the event, and the location of study records.

The study records must be transferred to an acceptable designee, such as another investigator, another institution, or to the Sponsor.

APPENDIX 1. METHODOLOGIES FOR STUDY OUTCOMES.

Healthspan

A subject's healthspan will be calculated using a proprietary algorithm housed within the prime health application. Briefly, subjects will answer a number of questions regarding their daily health habits, activities, and attitudes. These data will then be placed into a mathematical equation that uses data and statistics from numerous published studies regarding longevity and mortality risk. The outcome number is a subject's estimated "Healthspan," which describes their remaining healthy and active years of life. Importantly, this number can increase or decrease based on a subject's reported lifestyle changes at the end of the intervention period.

Biological Age

The subject's biological age will be estimated using the same proprietary formula used to estimate Healthspan. Briefly, biological age is different from chronological age, which simply reflects the number of years an individual has spent on Earth. Biological age, on the other hand, takes healthy lifestyle factors into account that may prematurely age individuals past their chronological age. Conversely, active and healthy users may find that their biological age is lower than their chronological age. Importantly, this number can increase or decrease based on a subject's reported lifestyle changes at the end of the intervention period.

Lifestyle Risk Factors

These risk factors are assessed by a number of questions pertaining to lifestyle habits that the subject must answer when enrolling in the application. As also extracted from the questionnaire.

Energy and Vitality

These outcome measures are subjective reports based on subject responses to specific questions within the application's questionnaires.

Strength and Endurance

Application users will be required to perform three objective performance tests to get accurate estimates of their healthspan and biological age. These performance tests include: *Upper Body Strength*: Upper body strength will be assessed using the push-ups to failure protocol. Users will be instructed via the application on correct form and technique for push-ups specific to their gender. They will then perform as many push-ups as possible before reaching concentric muscle failure. This number will be reported to assess their upper body strength.

Endurance: Endurance will be assessed using a one mile walk time. Subjects will perform this assessment at their own determined pace, which is obviously restricted by their physical ability. Running is allowed, but not all subjects will be able to run the full mile. Thus, walking is allowed in this assessment.

Lower Body Strength: Lower body strength will be assessed by chair get-ups to concentric muscle failure. Briefly, subjects must use a chair or a related sturdy surface that reaches the height of their patella. They must fully sit and return to start for each repetition. They will

continue to perform get-ups to concentric muscle failure. This number will be reported to assess their lower body strength.

Body Composition

Body composition will be measured using a previously validated digital scale (RENPHO Smart Scale) that will be delivered to participants upon enrollment in the study. The scale uses bioelectrical impedance to estimate body composition. This involves a low level electrical current being sent through the body; the user cannot feel, hear, or otherwise sense this electrical current. The rate at which the current passes through the body is then input into an algorithm to estimate body composition based on known electrical current rates in human body tissue.

Body composition will also be estimated by questions embedded within the application and a corresponding algorithm.

Blood Pressure

Blood pressure will be measured using a previously validated electronic blood pressure cuff (Oklar Cuff Model C02) that will be delivered to participants upon enrollment in the study. The blood pressure cuff is capable of executing blood pressure measurements with minimal input from the user. Blood pressure is reported as systolic over diastolic, and the user will input these numbers into the application questionnaire.

Daily Steps

Daily steps will be assessed using communication between the Pro2col application and the user's Apple Health or Google Fit application. Apple Health and Google Fit both collect daily step counts by way of accelerometry, gyroscopy, and global positioning systems (GPS) and these data will be transferred to and housed within the Pro2col application.

Depression

Symptoms of depression will be assessed using the Patient Health Questionnaire-9 (PHQ-9). This questionnaire is a previously validated tool that collects information about depression symptoms in users. The user answers nine questions relating to depression symptoms on a scale of 0-3, with 0 representing no issues at all, and 3 representing experiencing the symptom nearly every day. The user's total score is a summation of their responses, and is scored as follows:

1-4 Minimal depression5-9 Mild depression10-14 Moderate depression15-19 Moderately severe depression20-27 Severe depression

Importantly, users who score ≥ 10 arbitrary units on the PHQ-9 during baseline testing will fail to continue being eligible for the study. In this instance, a study staff member will contact the individual, explain the reasoning, and thank the subject for their time. Due to the remote nature of this study, it is impossible to partner with a mental health clinic for subject referrals. Subjects will be encouraged to speak with their primary care physician if they are

concerned about their score. An email script will be crafted to provide further information for this instance.

Quality of Life

Quality of life will be assessed by the previously validated 36-item Short Form survey (SF-36). The SF-36 houses a number of questions pertaining to various factors of quality of life. Subjects will answer questions in a variety of manners, from simple "yes" or "no" responses to Likert-adjacent scaled responses that allow the subject to select the answer that best corresponds to their attitudes and beliefs. The scoring instructions for the SF-36 can be accessed in the .pdf linked here.

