4. OUTCOMES MEASURE

- 4.1. Primary Outcomes these measures will be taken at week 0 (pre) and week 7 (post)
 - Healthspan, as assessed via a digital score within the application software.
 - **Biological Age**, as assessed via an algorithm sourced within the application.
 - Lifestyle Risk Factors, as assessed via questionnaires within the application.
 - Energy and Vitality, as assessed via questionnaires within the application.
 - Strength and Endurance, as assessed by performance measures including a timed mile walk/run, push-ups to exhaustion, and chair get-ups to exhaustion.
 - Body Composition, as assessed via a previously validated digital scale.
 - Blood Pressure, as assessed via an electronic blood pressure cuff.
 - Lifestyle Habits, as assessed by specific interfaces within the application and guided by an AI "coach."
 - **Daily Steps**, as collected via the Apple Health or Google Fit application on the subject's pre-existing personal device.

4.2. Secondary Outcomes – these measures will be taken at week 0 (pre) and week 7 (post)

- **Depression**, as assessed by the previously validated PHQ-9 subjective questionnaire.
- Quality of Life, as assessed by the previously validated SF-36 subjective questionnaire.

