6.2. Identity of Experimental Condition

The Experimental Condition involves the use of a novel smartphone application. This application provides a digital diagnostic score to calculate healthspan and biological age, along with AI and group community-based coaching dynamics. Subjects will be assigned a 4-6-week (28-42 days depending on subject availability for last testing day) progressive protocol designed to implement lifestyle changes and solidify adherable practices including the following:

- Daily practice of intermittent fasting, eating within a time restricted eating window ranging from 8 to 12 hours.
- Increased daily steps.
- Increased awareness of hydration practices.
- Journaling
- Adherence to a lower carbohydrate, higher-protein diet.
- Improved exercise habits.
- Stress management
- Sleep habits
- Improved lifestyle risk factors, like smoking and alcohol intake

The above factors are individualized based on subject responses to questionnaires within the application. An AI-based coach and application algorithms will then send users push notifications to improve adherence to their new lifestyle factors as well as provide feedback for their logged data entries. Specifically, the application users will be required to connect the Pro2col application with either the Apple Health or Google Fit application so that necessary data can be transmitted between these applications without user input. The application creates a personalized protocol by using responses from the embedded health questionnaire to establish baseline figures that the user will improve upon. For example, if a user reports walking between 4,001-5,000 steps daily, their program will start them at 4,000 steps in week 1, gradually increasing each week until they reach the program's goal (e.g., 10,000 steps). Below are the key elements used to generate an individualized protocol, with specific goals for this user:

Steps Goal: 10,000 Steps

Incremental Approach: Starting from the user's baseline, steps will gradually increase each week to reach the target of 10,000 steps over a 4-6-week period (28-42 days depending on subject availability for the last testing day).

Example:

Week 1: Starting at the baseline (e.g., 4,000 steps)

Week 2: 5,200 steps

Week 3: 6,400 steps

Week 4: 7,600 steps

Week 5: 8,800 steps

Week 6: 10,000 steps

Calorie Goal: Moderate Fat Loss

Caloric intake will be reduced on average by 250 calories from basal calorie needs.

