Hydration Goal: Subjects will have a target water consumption goal of 10 Cups of Water

Incremental Approach: Starting from the user's baseline (e.g., 5 cups), water intake will increase each week until reaching 10 cups over 6 weeks.

Example:

Week 1: 5 cups Week 2: 6 cups Week 3: 7 cups Week 4: 8 cups Week 5: 9 cups Week 6: 10 cups

Eating Window: 8 Hours

Incremental Approach: The eating window will decrease each week until it reaches an 8-hour window over 6 weeks. For example if they are currently eating 16 hours per day (for example 6 am to 10 pm), we would modify as such:

Example:

Week 1: 16-hour eating window

Week 2: 14-hour eating window

Week 3: 12-hour eating window

Week 4: 10-hour eating window

Week 5: 9-hour eating window

Week 6: 8-hour eating window

Subjects will also be awarded with points within the application for hitting their goal.

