7.2. BASELINE TESTING

Subjects who continue to be eligible for this study will then complete baseline testing. Subjective questionnaires will be provided to assess items such as current activity levels, nutrition habits, and lifestyle factors related to health and wellness. Enrolled and randomized subjects will also receive a blood pressure cuff and digital scale to record blood pressure and bodyweight/body composition, respectively. Moreover, subjects will complete electronic calculations to estimate their healthspan and biological age. Finally, subjects will perform three physical fitness tests, including:

- Timed one mile walk/run
- Push-ups (or modified push-ups for women) to exhaustion
- Chair get-ups to exhaustion

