7.3. INTERVENTION

Subjects will follow their assigned condition for 6 weeks. Subjects in the control group will be monitored by study staff but otherwise uninstructed in regard to activity and nutrition. Their adherence to the provided educational materials is entirely up to them. The experimental group will be initiated into a 4-6-week (28-42 days depending on subject availability for the last testing day) progressive protocol on the Pro2col app. They will receive daily updates, notification, and education regarding healthy habits such as exercise, hydration, and improved nutrition practices. An AI coach will be responsible for providing instructions and feedback to all application users.

7.4. **POST-TESTING**

Subjects who complete the 4-6-week (28-42 days depending on subject availability for last testing day) intervention and continue to be eligible for this study will then complete post testing. Subjective questionnaires will be provided to assess items such as current activity levels, nutrition habits, and lifestyle factors related to health and wellness. Enrolled and randomized subjects will also receive a blood pressure cuff and digital scale to record blood pressure and bodyweight/body composition, respectively. Moreover, subjects will complete electronic calculations to estimate their healthspan and biological age. Finally, subjects will perform three physical fitness tests, including:

- Timed one mile walk/run
- Push-ups (or modified push-ups for women) to exhaustion
- Chair get-ups to exhaustion

Finally, upon completion of the study (or early withdrawal), subjects will be directed to delete the investigational application from their smart device, and no further data will be collected.

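### Body composition is read at home on an impedance scale with no fixed reading conditions, while only the experimental arm is coached to change water, carbohydrate and meal timing

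*Combined protocol and SAP*

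**What the plan says.** Section 4.1 lists, among nine primary outcomes measured before and after the intervention, "Body Composition, as assessed via a previously validated digital scale". Appendix 1 explains the method: "The scale uses bioelectrical impedance to estimate body composition", and "The rate at which the current passes through the body is then input into an algorithm to estimate body composition". Body composition is thus inferred from an electrical reading. Appendix 1 adds a second estimate, calculated from questions in the app. Neither place says which component (fat percentage, fat mass or lean mass) is to be analysed, or which estimate counts as primary.

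Sections 7.2 and 7.4 have subjects use a cuff and scale "to record blood pressure and bodyweight/body composition, respectively". Section 5.1 makes clear that no visit to a facility is needed, so these readings are unsupervised. None of these sections sets conditions for the reading.

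Section 6.2 describes the experimental programme. It includes "Adherence to a lower carbohydrate, higher-protein diet", an eating window that narrows to 8 hours, and a hydration goal: "Subjects will have a target water consumption goal of 10 Cups of Water". In the worked example, "water intake will increase each week until reaching 10 cups over 6 weeks", starting from 5 cups.

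The other arm receives American Heart Association and USDA materials. Section 7.3 says: "Subjects in the control group will be monitored by study staff but otherwise uninstructed in regard to activity and nutrition".

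**The concern.** An impedance scale infers tissue composition from how current passes through the body. From how the method works, the estimate may depend on body water and on what has recently been eaten or drunk. Three parts of one arm's programme bear on exactly those things, and in the section 6.2 examples the targets are furthest from the starting habits in week 6, just before post-testing.

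Randomisation balances the arms at baseline. It does not protect against a measurement error that the assigned programme itself produces, and a larger sample does not dilute such an error. If the conditions of the reading are left to each subject, part of any between-arm difference in this primary outcome could reflect recent intake and not tissue. Uncontrolled readings cannot be put right afterwards, so the time to act is before the first baseline reading.

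**Working it through.** **1. The plan's own figure.** Section 10.1 gives 50 subjects for an effect size of 0.8. With two-sided alpha 0.05, and with 80% power and 1:1 allocation assumed because the plan states neither, n per arm = 2(1.960 + 0.842)² / 0.8² = 24.5. That rounds up to 25 per arm, or 50 in total. The exact t-test needs 26 per arm. The figure reproduces, but it concerns habits such as daily steps. The plan gives no effect size, SD or measurement error for body composition.

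**2. The texts side by side.**
- Measurement: current reading entered into an algorithm, taken at home (Appendix 1, sections 5.1, 7.2, 7.4).
- Experimental arm: water target of 10 cups, less carbohydrate, eating window down to 8 hours (section 6.2).
- Control arm: published materials, followed or not as the subject chooses (sections 6.3, 7.3).
- Reading conditions: none stated in Appendix 1 or in sections 7.2 and 7.4.

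The eating window matters separately from the diet. In the section 6.2 example it goes from 16 hours to 8, so the daily gap without food goes from 24 − 16 = 8 hours to 24 − 8 = 16 hours. At any given clock time, a coached subject and a control may therefore be at different points relative to their last meal.

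**3. Illustration of the consequence.** Assume the true between-arm difference is zero and that PRO readings carry a net shift of b, in SD units of change. The documents give no value for b, so a range is shown. Section 10.3.1 names paired t-tests. For two independent groups I use the two-sample t-test, two-sided at 0.05 (sidedness is not stated). With n per arm, df = 2n − 2 and noncentrality = b√(n/2). The chance of p < 0.05 is the noncentral-t probability beyond the critical value. At n = 25 and b = 0.5, for example, the noncentrality is 0.5 × √12.5 = 1.77 on 48 df, which gives 41%.

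| Assumed shift b | 20 per arm | 25 per arm | 100 per arm |
|---|---|---|---|
| 0 | 5% | 5% | 5% |
| 0.1 | 6% | 6% | 11% |
| 0.2 | 10% | 11% | 29% |
| 0.3 | 15% | 18% | 56% |
| 0.5 | 34% | 41% | 94% |

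Twenty per arm is the completer minimum in section 5.1. Twenty-five per arm is the section 10.1 sample. One hundred per arm is the enrolment ceiling of 200 split equally, with no dropout. The table shows what a shift of a given size would do. It is not evidence that a shift of any size exists.

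**The case against.** The strongest counter-argument is that the causal link is not in the documents. They do not say that more water or less carbohydrate changes this scale's reading, that body water would change in these subjects over 4 to 6 weeks, or how the algorithm responds. Two influences acting together might offset each other. At a shift of 0.1 SD the error rate at 25 per arm is 6%, close to nominal. All of this stands. A reader might infer that the artefact is present, follows treatment and cannot cancel. The documents support only that the plan leaves room for it.

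The exposure can also be overstated. The rise from 5 to 10 cups is one example; section 6.2 individualises targets from questionnaire answers, and a subject already near 10 cups would change little. Controls receive dietary guidance too, although following it is optional. Section 5.2.1 requires everyone to be willing to download the app, but sections 5.1 and 7.3 give the coached programme to the experimental arm only. The contrast in coaching stands; its size in practice is unknown.

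The scale is described as previously validated. That is a general statement, and nothing in the plan says it covers change over time when the arms are coached differently on hydration. The app-based second estimate does not settle the matter either: it comes from questions answered by unblinded subjects.

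Finally, this is a pilot with an exploratory aim, and body composition did not drive the sample size. That limits the weight of the point but does not remove the case for a nearly free instruction.

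**Conclusion.** The concern holds as a gap in measurement procedure. A primary outcome is estimated by impedance under uncontrolled home conditions, while one arm alone is coached on water, carbohydrate and meal timing. Readings could differ between arms partly through recent intake. Neither the size nor the direction can be found from the documents. The illustrative error rate at 25 per arm is 5% to 41% for an assumed shift of 0 to 0.5 SD. It rests on a true difference of zero, one net shift in PRO only and a two-sample test.

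Three stronger readings are not supported:
- A reader might take the 94% in the table as the risk the trial runs. It needs the largest assumed shift and 100 analysed subjects per arm, and nothing in the plan supports the first or promises the second.
- A reader might say the result would be mistaken for fat loss. The plan names no fat variable and states no such interpretation.
- A reader might conclude that body weight should become the main variable, or that fat loss should never be accepted without weight loss. Weight also carries body water, so it does not separate water from fat. The programme also includes exercise and higher protein, so fat could fall at stable weight.

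The severity is minor: a worthwhile improvement, not a flaw that undermines the trial.

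**What to change.** In Appendix 1 (Body Composition) and in sections 7.2 and 7.4, add one instruction for all subjects in both arms. The scale reading is to be taken at the same time of day at both tests, before eating or drinking, before the fitness tests, and on the same delivered scale. The last item also clears up section 7.4, which reads as though a scale is sent again at post-testing, whereas Appendix 1 has it delivered on enrolment.

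In the analysis, report scale body weight beside the impedance value. Label the latter as an impedance estimate that may reflect a sustained difference in body water.

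The cost is one extra instruction for subjects and a line of labelling. The change reduces bias and noise from recent intake. It does not remove a lasting difference in body water, and the time since the last meal may still differ where eating windows differ, so the label is needed as well as the instruction.
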